6.2 PROCEDURE

6.2.1 SET UP

The set-up is predetermined prior the start of data collection.

The nGVS machine, electrical stimulator, and associated leads/electrodes will be set up as below:

nGVS through 1X1 Galvanic vestibular stimulator

- Parameters set for the noisy galvanic stimulation (subthreshold)@ Waveform: Random Noise; Intensity: 1 mA, Polarity: Bipolar; Durations: 20 minutes.

Electrical stimulation through Digitimer DS7A

- Parameters set for the electrical stimulation; Voltage: 400(Vmax); Pulse width: 2000 us(microseconds) (I have chosen 2000 microseconds because it is 2 milliseconds, and 2 milliseconds is indeed 0.002 second which is bigger in turning the trigger and is not faint than the 500 microsecond). Also 500us is really brief pinprick and fires of the nerve; Intensity: as per staircase procedure.

Force plates

COP sway length was measured for 30 s twice at three timepoints: baseline, during intervention (+5 min) and post intervention (+ 5 min), at 100 Hz, in standing by VALD Performance Force decks dual force plate system. The average COP sway length value will be calculated.

6.2.2 PARTICIPANT ARRIVAL

The participant will be asked to sit comfortably. Consent will be documented, and all procedures will be explained the participant, as follows:

The researcher will prepare the skin behind the ear by rubbing it with alcohol swab to take any extra body oil and allowing to dry. The nGVS electrodes will be applied behind both ears on the mastoid process and the Ambu blue sensor ECG electrodes on the lateral border of the right foot, respectively.

Instructions to participant:

- *This is an electrode. I am going to place behind your both ears. I will prepare the skin by cleaning it with alcohol swab to get rid of body oil. I will be placing two of these electrodes, one each on your left and right ear.*

- *This is an electrode. I am going to place on outer border of your right foot. I will prepare the skin by cleaning it with alcohol swab to get rid of any body oil. I will be placing 4 of these electrodes on the outer border of your right foot.*

- *Is it ok for me to apply both types of electrodes now?*

Then the “sensory threshold” will be determined using a staircase procedure (Ellaway et al., 2012; Schmidt et al., 2013) through the Digitimer. This is followed by measurement of the detection rate using a stimulus below the -10% threshold.

6.2.3 SETTING SENSORY – THRESHOLD THROUGH STAIRCASE PROCEDURE

To setup the threshold for somatosensory detection task (SSDT) measurements, a staircase procedure will be used. This involves determining the sensory threshold. The sensory threshold is termed the 100% threshold. To initially calibrate the stimulus intensity for each potential participant, the current intensity will be delivered through the Digitimer at 1mA and increasing in steps of 0.1 mA until the participant responds YES, indicating a tingling sensation (first threshold) to the researcher. The stimulus intensity will be decreased until the participant reports NO, indicating the disappearance of sensation (second threshold). This procedure will be repeated a second time and the median of these values will be defined as the sensory threshold of the participant (K Oppenlander et al., 2015).

To record the sensory threshold, the participant is required to stand with their feet together.

The following instructions given to participant:

- *Please stand still.*
- *Now we are going to measure how strong you feel the current on your feet.*
- *I will do this two times.*
- *Ready to start?*
- *Are you ready?*
- *Just let me know when you feel the sensation by saying Yes/No*

6.2.4 OUTCOME MEASUREMENT PROCESS THROUGH SOMATOSENSORY SIGNAL DETECTION TASK (SSDT)

This outcome measurement process involves carrying out a SSDT. The SSDT will be administered using a repeated-measure design before, during and after delivering each intervention (real nGVS or sham). During the SSDT, electrical stimuli will be delivered to the lateral border of the right foot through electrical stimulation (Digitimer, DS7A) to identify the threshold and -10% (Ferre et al., 2011). The different stimulus type trials which will be delivered to the right foot during the SSDT are A (above: 10% threshold, i.e., 110%), B (below: -10% threshold, i.e., 90%) and C (sham in which no stimulus will be present i.e., 0%). The trials will be delivered randomly to avoid any learning effect by the participant. Participants will report whether they can detect each trial. Through these measurements, we will determine the following outcome measures:

- True positive rate (TPR): The number of tactile stimuli a person can feel when stimulation is set at 90% sensory threshold.
- True negative rate: When a person receives a catch (no stimulation), they say “no”
- False positive rate: When a person receives a catch (no stimulation), they say “yes”
- False negative rate: When a person receives a 110% stimulus, they say “no”
- COP sway length in millimetres

6.2.5.1 BEFORE, DURING, AND FOLLOWING INTERVENTION

As mentioned above in the SSDT section, overall, 70 trials (explained below) will be administered to the lateral border of the right foot. A, B and C will be randomised. The participants will be blinded throughout the task.

- 30 trials of A (above, at +10% threshold, i.e., 110%) on the right foot
- 30 trials of B (below, at -10% threshold, i.e., 90%) on the right foot
- 10 trials of C (catch in which no signal will be present i.e., 0%) on the right foot

The trials will be delivered via programmed computer. The participant will indicate whether they have felt the stimulus, and this will be recorded. Each trial will last for 13 seconds (Kuzyk & Schemitsch). The following will be explained:

- *Please stand still.*
- *Now we are going to deliver small pulses to your foot and record when you can feel them.*
- *We will test you for about 15 minutes, and you will hear regular warning signals to let you know to pay attention. You may or may not feel something after the signal and we want you to indicate if you feel something by saying Yes or No after the warning signal.*
- *Ready to start.*
- *Are you ready?*
- *Please indicate if you feel something.*

Whilst participant completing sensory testing, and responding Yes/No, during the last 2 minutes of sensory testing, the COP sway length will be measured twice in standing at each timepoint for 30 seconds with 5 seconds in between the two consecutive measurements on the force plates (VALD Performance Force decks dual force plate system).. During the experiment, the fade-in and fade-out times will be set at 5 seconds and COP sway will be measured for 30 seconds after the fade in time. The following will be explained.

- *Please could you come on these force plates and stand still.*
- *Could you please place your feet on the stickers below.*
- *Now we are going to measure your balance.*
- *You don't need to do anything as the force plates will automatically measure your data.*
- *We are also delivering small pulses to your foot as we did before.*
- *Say yes/No after the warning signal.*

6.2.5.1 FOLLOWING INTERVENTION

As mentioned above in the SSDT section, overall, 70 trials (explained below) will be administered to the lateral border of the right foot. A, B and C will be randomised. The participants will be blinded throughout the task.

- 30 trials of A (above, at +10% threshold, i.e., 110%) on the right foot
- 30 trials of B (below, at -10% threshold, i.e., 90%) on the right foot
- 10 trials of C (catch in which no signal will be present i.e., 0%) on the right foot

The trials will be delivered via programmed computer. The participant will indicate whether they have felt the stimulus, and this will be recorded. Each trial will last for 13 seconds {warning (2 seconds) followed by trigger (1 second) followed by break (10 seconds)}. The following will be explained:

- *Please stand still.*
- *Now we are going to deliver small pulses to your foot and record when you can feel them.*
- *We will test you for about 15 minutes, and you will hear regular warning signals to let you know to pay attention. You may or may not feel something after the signal and we want you to indicate if you feel something by saying Yes or No after the warning signal.*
- *Ready to start.*
- *Are you ready?*

- *Please indicate if you feel something.*

6.2.6 INTERVENTION DELIVERY FOR CONDITION 1 OR 2

The participant will be standing comfortably. The stimulator and computer screen will never be visible for the participants.

Prior to the intervention, the following is explained to the participant:

- *The intervention involves applying some electrical stimulation to the electrodes behind your ears.*
- *I will turn up the stimulation until you can feel something behind your ears. Please let me know when you feel something. It should not hurt as it is very weak current, but please let me know if it does.*
- *Is it ok if I start now?*

The researcher will start the stimulation slowly by turning the current value up through adjustor switch called “RELAX” on the machine until the participant will perceive a tingling behind the ears. This intensity and location will be used in the subsequent intervention for the total of 20 minutes duration.

For the nGVS

The participant will receive 20 minutes of nGVS.

For the control protocol (Sham)

The participant will receive 20 minutes of sham for the sham stimulation, the stimulation will be started and then stopped without any notice to participant.

NOTE: When the researcher is not collecting data during the stimulation is on, the participant will be allowed to move the foot to avoid fatigue or discomfort from standing too still.

6.3 DATA COLLECTION:

All data will be collected using a combination of written data collection forms and computer software (MATLAB, Signal).

6.4 DATA ANALYSIS:

The data processing and analysis will be done by blinded assessor.

7. Safety Considerations

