In 2013, Ferrè and colleagues used the non-invasive technique of GVS on somatosensory perception by administering different GVS polarities. The process involved using a small weak direct current through electrodes placed on the mastoid process. It is known that GVS can regulate the firing rate of vestibular afferents by changing the stimulation polarity, and can increase the firing rate through cathodal currents and decrease through anodal currents (Ferrè et al., 2013; Fitzpatrick & Day, 2004). According to a study by Ferre and colleagues (2013), GVS activates the vestibular cortical projections by inducing excitatory postsynaptic potentials (EPSPs) in both tactile and vestibular neurons. GVS through the bipolar binaural way causes firing of both vestibular organs, thus imitating head motion in space. A recent development of GVS is nGVS, which uses subsensory stimulation levels of GVS delivered along with a gaussian noise signal to enhance weak sensory input and facilitate information processing in sensory systems. nGVS also has the potential to influence postural responses.

It is well known that the vestibular system imparts the foundational control signals for position, motion, and postural control, relative to the extrinsic environment. All these complex functions need to incorporate vestibular inputs with signals from the various sensory systems. Somato-sensation is one such sensory modality. Some evidence in healthy people (Ferre et al., 2013) suggests that supra-threshold galvanic vestibular stimulation (GVS) when delivered through different polarities has specific facilitatory effects on somatosensory detection. (Ferre et al., 2013). As supra-threshold GVS is uncomfortable and can cause adverse effects such as dizziness and vomiting, it is more feasible to deliver nGVS which delivers GVS with a sub-threshold weak current.

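### The nGVS dose is fixed at a subthreshold 1 mA in section 6.2.1 but titrated to felt tingling in section 6.2.6, so the protocol holds two incompatible dose rules

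*Protocol*

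**What the plan says.** Section 6.2.1 (Set up) opens with "The set-up is predetermined prior the start of data collection". It then gives "Parameters set for the noisy galvanic stimulation (subthreshold") and lists "Waveform: Random Noise; Intensity: 1 mA, Polarity: Bipolar; Durations: 20 minutes". As written, that is one intensity for every participant.

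Section 6.2.6 (Intervention delivery for condition 1 or 2) describes a ramp with an adjustor on the machine, continued "until the participant will perceive a tingling behind the ears. This intensity and location will be used in the subsequent intervention". The full closing sentence is "This intensity and location will be used in the subsequent intervention for the total of 20 minutes duration". The script read to participants repeats the rule: "I will turn up the stimulation until you can feel something behind your ears". No reduction below the felt level follows, and no maximum is stated.

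The background before section 3 describes nGVS as a technique "which uses subsensory stimulation levels of GVS delivered along with a gaussian noise signal". Both the background and the Rationale in the summary table prefer it to supra-threshold stimulation because "it is more feasible to deliver nGVS which delivers GVS with a sub-threshold weak current".

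On sham, the Method in the summary table says that electrodes are applied and nothing is delivered. Section 6.2.6 says the current is started and then stopped without the participant being told. Section 5.1 calls the study double blinded.

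**The concern.** Dose delivery belongs in the protocol, and here it depends on which section the operator follows. One section gives a common, predetermined 1 mA described as subthreshold. The other gives an individual current at the level the participant can feel. If operators differ, the active dose varies without a rule. If all follow 6.2.6, the trial tests a felt-level current while describing it as subsensory, which departs from the stated reason for choosing nGVS. In either case a reader cannot tell which dose the comparison with sham applies to.

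A possible further consequence is weaker participant blinding. In the active session a current set at the felt level stays on, while in the sham session it is switched off. This would bear mainly on the measurement taken during stimulation (secondary objective 1). The primary true positive rate is measured after stimulation has ended in both sessions, so no direct effect of this kind on it is claimed.

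**Working it through.** The contradiction comes from setting the text side by side. The arithmetic only shows how far apart the two rules can be.

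**Step 1: the two rules.**

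- Rule A (6.2.1): dose = 1 mA for everyone.
- Rule B (6.2.6): dose = T, where T is the participant's own tingling threshold in mA.

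Rule A comes with the label subthreshold. Rule B ends at perception, and that intensity is carried into the intervention.

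**Step 2: does another section settle it?** No. The Method in the summary table says only that real nGVS lasts 20 minutes and gives no intensity. The staircase procedure in 6.2.3 sets the foot stimulus, not the current behind the ears.

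**Step 3: size of the difference.** The protocol states no value of T, so T = 0.5 to 2.0 mA is an assumed range.

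- Rule B relative to rule A = T / 1.
- Rule A as a share of the participant's own threshold = 1 / T.
- Rule B as a share of the participant's own threshold = T / T.

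| T (mA, assumed) | Rule B relative to rule A | Rule A as share of own threshold | Rule B as share of own threshold |
|---|---|---|---|
| 0.5 | 50% | 200% | 100% |
| 0.8 | 80% | 125% | 100% |
| 1.0 | 100% | 100% | 100% |
| 1.25 | 125% | 80% | 100% |
| 2.0 | 200% | 50% | 100% |

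The rules deliver the same current only at T = 1 mA. Rule B sits at the felt level for every T. Rule A is below the felt level only where T exceeds 1 mA, so a fixed 1 mA is not guaranteed to be subsensory either.

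**Step 4: could 1 mA be a ceiling on the ramp?** The dose would then be min(T, 1).

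- For T at or below 1 mA, the dose is T, still 100% of the felt level.
- For T above 1 mA, the ramp stops before tingling, so the endpoint that 6.2.6 requires is never reached.

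A ceiling therefore does not reconcile the sections.

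**The case against.** The strongest case on the other side has four parts.

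- **Predetermined need not mean identical for all.** The same section 6.2.1 lets the staircase procedure set the foot stimulus intensity, which is individual. This is fair, and the word adds little. The explicit 1 mA carries the argument without it.
- **Subthreshold may mean below a vestibular threshold.** The Rationale contrasts it with supra-threshold stimulation that causes dizziness and vomiting, and a just-felt tingling under the electrode could be subthreshold in that sense. This reading is arguable for that one word. But the background says subsensory and the protocol nowhere separates a skin threshold from a vestibular one. Even if the reading is granted, a fixed 1 mA and titration to tingling remain different doses.
- **The range only restates an assumption.** This is correct: 50% to 200% is the assumed T divided by 1 mA, and T / T = 100% is true by definition. It also describes the moment of setting, because the document does not say whether tingling persists after onset. The contradiction needs none of these figures.
- **The randomised comparison survives.** Under either rule each participant receives active and sham, and an operator would probably follow the explicit steps in 6.2.6. The within-person contrast does stand. What is lost is knowledge of the dose it refers to, and following 6.2.6 means delivering something other than the intervention described in 6.2.1 and the background.

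On blinding, the ramp used in both conditions, the unannounced stop and the hidden stimulator all reduce the risk without removing it. The two sham descriptions could roughly fit together if the start is brief, but no on-time is given.

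**Conclusion.** The concern holds. Sections 6.2.1 and 6.2.6 state different dose rules for the experimental intervention, nothing in the protocol reconciles them, and the rule in 6.2.6 sets the current at a felt level, contrary to the subsensory description. This follows from the text alone. The size of the gap in mA cannot be taken from the document: over an assumed threshold range of 0.5 to 2.0 mA, the 6.2.6 dose is 50% to 200% of the 6.2.1 dose. The point must be fixed because it leaves the tested dose undefined. The possible loss of blinding during stimulation is secondary, and the sham wording is minor.

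**What to change.** 1. Amend 6.2.6, including the participant script, to one dose rule that agrees with 6.2.1 and the subsensory description. Two forms would do:
   - a fixed 1 mA, stating what is done if the participant feels it; or
   - a stated fraction below the individual tingling threshold, capped at 1 mA or another stated value.

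   If the team does intend titration to threshold, correct 6.2.1 and the subthreshold and subsensory wording in the Rationale and background instead.
2. Record the delivered mA at each session, unless the data collection forms (not shown) already do so.
3. Minor: align the sham text in the Method and 6.2.6, so that both describe the shared ramp, if it is kept, followed by switch-off after a stated time.

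The cost is a few lines of wording in 6.2.6 (or in 6.2.1, the Rationale and the background), one line on sham in the Method, and one recorded value per session. The design, sample size and analysis are unchanged.

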7.1 ELECTRODES

Electrodes may cause temporary skin irritation and redness. Participants will be offered aloe vera lotion following electrode removal.

7.2 ADVERSE EVENTS

Any adverse events will be recorded in an adverse event form and reported to [name] (primary supervisor) for appropriate follow up.

8. Follow-Up

When the study results have been interpreted, a summary of the study findings will be sent to the participants.

9. Data Management

Screening and consent forms will be kept in a locked filing office. After consent, participants will be given a unique participant code, and all subsequent data will be recorded against this code. Computer files will be saved in a folder on AUT's hard drive that is only accessible to [name], [name] and [name], and on a USB hard drive that will be stored in a locked cabinet in [name]'s office. Data collection sheets will be kept in a locked cabinet in [name]'s office.

10. Sample size calculation

Based on data collected in previous study conducted by the team on healthy young adults "Investigating the effects on nGVS on somatosensory perception in healthy adults, a sample size of 27 participants is required after seeing the normality and order effect.

11. Statistical analysis

The SSDT results will be analysed using Signal detection analysis (Macmillan et al., 1991). The number of HITS (number of stimulus-present trials in which participant will say 'YES'), FALSE ALARMS (number of stimulus-absent catch trials in which participants will say 'YES'), MISSES (number of stimulus-present trials in which participant will say 'NO') and CORRECT REJECTIONS (number of stimulus-absent catch trials in which participant said 'NO') will be considered.

Further, a mixed between within subjects' analysis of variance (ANOVA) will be conducted to assess the impact of two different interventions (nGVS and sham) on the participant's scores of perceptual sensitivity d' and response bias (C) across three timepoints (Pre intervention, during intervention and post intervention). The normative check will be conducted using distribution before proceeding for ANOVA. A longitudinal analysis of covariance will be conducted to evaluate the primary null hypothesis that the true positive rate is equal across the two conditions. For this purpose, a linear mixed regression model will be constructed. The model will be estimated post-intervention outcomes while adjusting for the pre-intervention outcomes. To account for repeat measures from the same participants, the model estimation will be done as a participant-wise random intercept. The null hypothesis will be tested by statistically comparing the model-estimated post-intervention means using t-tests. The statistical significance level will be set at 0.05. These means and their differences will be reported along with their 95% confidence intervals

A statistical analysis will be carried out using SPSS software. Data from each outcome measure will be analysed using two-way repeated measures ANOVA and post hoc t-tests to explore main effects and interactions.

The mean difference of Sway path length parameter will be analysed.

12. Quality Assurance

The research assistant will be trained in the protocol (if required) by [name].

13. Recruitment

If all participants have not been recruited by six months, recruitment will be ceased, and data collection/analysis will continue with those already recruited.

14. Project Management

[name]	Responsible for overall management of the research including organising appointment and supervision of RAs, recruitment, scheduling sessions, data collection, data processing, and data analysis.
Research Assistant	Responsible for assisting with data collection in lab sessions and doing randomisation and delivering the interventions or control as required.
[name]	Supervising project (primary supervisor).
[name]	Supervising project (secondary supervisor). Overseeing data collection processes.
[name]	Supervising project (Advisor).

15. Screening

The Researcher will screen all potential participants using a screening form.

Forms attached separately.

16. Informed Consent

All participants will be given an information sheet and will be asked to sign a consent form. Forms attached separately.

17. Budget

The following costs will be funded through previously sourced EMC funding and from FHES PhD student funds (AUT).

Resources Required	Quantity	Estimated Costs	Funding Agency
Consumables:			
Electrodes (ECG Mini Electrodes)	2 Packets	\$60	HRRI Funds
Gel Whiteleys	1	\$25	
Fixomull stretch (5cm X 10m) Whiteleys	2	\$27	
Paper envelope for randomisation	1 Packet	\$2	

Medi-Alcoholic Swabs (200/pack) Whiteleys Plastic container to store electrodes	1	\$5 \$10	
Countdown vouchers	27 participants x 2 visits=54	\$1080	EMC funds
Research Assistant	50 hours (includes 3 hours training) X \$23.30 60min X 2 sessions x 27 participants=3240 min =54 hours X \$24.50	\$ 1323	EMC funds
Printing and Photocopying			
Information sheets	30 sheets		FHES Doctoral Funds
Consent sheets	30 sheets	\$30	
Data collection sheets	30 sheets		
TOTAL		\$ 2562	

1. References

- Fasold, O., von Brevern, M., Kuhberg, M., Ploner, C. J., Villringer, A., Lempert, T., & Wenzel, R. (2002). Human vestibular cortex as identified with caloric stimulation in functional magnetic resonance imaging. *Neuroimage*, *17*(3), 1384-1393.
- Ferre, E. R., Bottini, G., & Haggard, P. (2012). Vestibular inputs modulate somatosensory cortical processing. *Brain Structure and Function*, *217*(4), 859-864.
- Ferrè, E. R., Bottini, G., & Haggard, P. (2011). Vestibular modulation of somatosensory perception. *European Journal of Neuroscience*, *34*(8), 1337-1344.
- Ferre, E. R., Bottini, G., Iannetti, G. D., & Haggard, P. (2013). The balance of feelings: vestibular modulation of bodily sensations. *Cortex*, *49*(3), 748-758.
- Ferrè, E. R., Day, B. L., Bottini, G., & Haggard, P. (2013). How the vestibular system interacts with somatosensory perception: a sham-controlled study with galvanic vestibular stimulation. *Neuroscience letters*, *550*, 35-40.
- Fitzpatrick, R. C., & Day, B. L. (2004). Probing the human vestibular system with galvanic stimulation. *Journal of applied physiology*, *96*(6), 2301-2316.

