5.3 EXCLUSION CRITERIA

- Diagnosed vestibular disorder or active BPPV
- Fallen more than twice in the past 6 months (Gaebler et al, 1993)
- Any diagnosed neurological impairment
- Medical conditions that are contraindicated with nGVS such as implants in head, neck, ankle or right foot, epilepsy, cardiac arrhythmias, unexplained recurring headaches, diabetic neuropathy (Thakral et al., 2013).
- Medical conditions that are cautioned with electrical peripheral stimulation of the foot such as metal implants in the area, skin lesions (Kuzyk & Schemitsch, 2009)
- Medical conditions that might affect the testing such as such as speech dysfunction, cognitive impairment
- Any allergic skin reaction to sticking plasters as a similar substance is used in the foot electrodes and to fix the nGVS electrodes

5.4 PRIMARY OUTCOME MEASURE:

- True positive rate (TPR): The electrical stimulation will be applied at 10% below threshold, i.e., at 90% sensory threshold for 30 times. The number of times the participant correctly identifies the stimuli will be scored out of total 30 number of trials (Bottini et al., 2013; Ferre et al., 2012; Ferrè et al., 2011; Ferre et al., 2013).

5.5 SECONDARY OUTCOME MEASURES:

- True negative rate (specificity): This will be the number of trials in which the participants received a catch (i.e., no stimulation), and said "NO". (Ferre et al., 2011).
- False positive rates: This will be the number of trials in which the participants received a catch and said, "YES".
- False negative rate: This will be the number of trials in which 110% stimulus is given and participants say 'no'.
- Perceptual sensitivity (d')
- Response bias (C)

[figure not shown]
Signal detection analysis (Macmillan et al, 1991) will be used to interpret the data for the SSDT task. That is a reason for the plan to measure three categories (as described above) according to the participant's responses.

- COP sway length will be obtained from VALD Performance Force decks dual force plate system.

5. Methodology

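### Hits and misses for d' and C are defined over both stimulus intensities, while the primary true positive rate uses the 90% trials only

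*Protocol*

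**What the plan says.** Section 11 defines the signal detection counts as "HITS (number of stimulus-present trials in which participant will say" yes and "MISSES (number of stimulus-present trials in which participant will say 'NO", with "FALSE ALARMS (number of stimulus-absent catch trials in which participants will say 'YES" supplying the false alarms. It then analyses d' and C by ANOVA across conditions and three timepoints.

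Section 5.4 defines the primary TPR at one intensity: "The electrical stimulation will be applied at 10% below threshold, i.e., at 90% sensory threshold for 30 times", "scored out of total 30 number of trials". Section 5.5 defines the false negative rate at the other intensity, as the "number of trials in which 110% stimulus is given and participants say" no. Section 6.2.4 and the method summary at the front of the protocol repeat both definitions.

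Section 6.2.5.1 sets the trial mix: 30 trials at 110%, 30 at 90%, and "10 trials of C (catch in which no signal will be present i.e., 0%) on the right foot".

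Section 5.5 lists d' and C as secondary outcomes. It says that signal detection analysis is the means of interpreting the task data and the reason for having three trial categories.

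**The concern.** The same yes/no answers carry three definitions of detection: TPR on the 90% trials, false negatives on the 110% trials, and hits and misses on both. TPR and the false negative rate are not complements, and neither equals a section 11 quantity.

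This matters because TPR is a raw yes rate. A participant who becomes readier to say yes raises it without perceiving more. Separating the two is what d' and C are for, but they can do so for the primary outcome only if computed on the same trials. A pooled d' describes an average over two intensities, one of which the primary outcome leaves out. If the 110% trials sit near ceiling, the pooled score also dilutes whatever happens at 90%.

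**Working it through.** **Trial counts (section 6.2.5.1).** 30 + 30 + 10 = 70, which matches the stated 70 per block. Stimulus-present trials: 30 + 30 = 60. The primary outcome's share of them is 30/60 = 50%.

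**Formulas.** Pooled hit rate H = (p90 + p110)/2. Sensitivity d' = z(H) − z(F), bias C = −[z(H) + z(F)]/2, where F is the false alarm rate. If F does not change, it cancels from the change in d'.

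**Assumptions.** The protocol gives no hit or false alarm rates. I take p90 from 0.30 to 0.50, p110 from 0.80 to 0.98, and F = 0.10 unchanged.

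**The level differs.** With p90 = 0.40, p110 = 0.90 and z(0.10) = −1.282:
- 90% trials only: z(0.40) = −0.253, so d' = 1.03 and C = 0.77.
- Pooled: H = 0.65, z = 0.385, so d' = 1.67 and C = 0.45.

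**The change differs.**

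| p90 | p110 | d' change, 90% only | d' change, pooled | ratio |
|---|---|---|---|---|
| 0.30 to 0.40 | 0.80 fixed | 0.271 | 0.128 | 0.47 |
| 0.30 to 0.40 | 0.90 fixed | 0.271 | 0.132 | 0.49 |
| 0.40 to 0.50 | 0.90 fixed | 0.253 | 0.139 | 0.55 |
| 0.50 to 0.60 | 0.98 fixed | 0.253 | 0.163 | 0.64 |
| 0.40 to 0.50 | 0.90 to 0.95 | 0.253 | 0.212 | 0.84 |
| 0.40 to 0.50 | 0.80 to 0.90 | 0.253 | 0.271 | 1.07 |

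With p110 fixed, the pooled hit rate changes by exactly half (0.10 becomes 0.05), and the d' ratio runs from 0.47 to 0.64. For a 0.10 gain at 90%, a 0.05 gain at 110% gives d' ratios of 0.71 to 0.91, and a 0.10 gain at both gives 0.96 to 1.14. An equal shift of 0.25 on the z scale at both intensities gives 0.56 to 0.86.

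**Noise differs too.** For the hit rate, with binomial variance only, p90 = 0.40 rising by 0.10 and p110 fixed at 0.90:
- 90% variance: 0.40 × 0.60/30 = 0.0080.
- Pooled variance: (0.24 + 0.09) × 30/3600 = 0.00275.
- Standardised ratio: (0.05/√0.00275)/(0.10/√0.0080) = 0.85.

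It is 0.77 with p110 = 0.80 and 0.96 with p110 = 0.98.

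**What a criterion shift does to TPR.** Fix d' at 1.0 and start at F = 5%. TPR is Φ(−1.645 + 1.0) = 26%. Move the criterion by 0.3 and TPR becomes Φ(−0.345) = 36.5%, about 3 more of 30 trials. F becomes Φ(−1.345) = 9%, only 0.4 more of 10 catch trials. Raw catch counts would barely show it.

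**Zero false alarms.** P(0 of 10) = (1 − F)^10: 60% at F = 5%, 35% at 10%, 11% at 20%. In such a block z(F), and with it d' and C, is not finite without a correction.

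**The case against.** - **Pooling is inferred.** No sentence says that the intensities are combined, and a figure beside d' and C in section 5.5 is not shown. It may hold formulas. That stands as a caution. But the visible section 11 text is the operative definition of a hit, and nothing legible restricts it to one intensity.
- **The primary analysis is untouched.** TPR is defined consistently at 90% and has its own mixed model. The protocol does not call d' or C a check on the primary result. This stands.
- **Bias is not left unexamined.** False positives, true negatives and C are listed outcomes. In a randomised, sham-controlled crossover described as double blinded, criterion drift common to both conditions cancels from the contrast; only differential drift biases it. This stands, though 10 catch trials make the catch-based outcomes imprecise.

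A reader might infer that pooling halves any effect. That is exact only for the raw hit rate, and only if the 110% trials do not respond at all, which the protocol does not say. Nor does it mean a halved standardised effect.

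A reader might also infer that d' will be undefined somewhere for nearly every participant. Across six independent blocks the chance of at least one zero is 99.6%, 92% and 49% at false alarm rates of 5%, 10% and 20%, so the inference needs a low rate that the protocol does not give. Section 11 neither describes nor excludes a correction, and a statistical analysis plan could supply it.

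**Conclusion.** The point holds as a mismatch of definitions that affects secondary outcomes. Followed literally, section 11 computes d' and C on 60 trials at two intensities, and these do not measure sensitivity and bias at the intensity of the primary outcome. If the effect is confined to the 90% trials, the pooled d' change is about 0.5 to 0.6 of the 90%-only change; if the 110% trials respond too, the loss shrinks and can vanish. These ratios rest on assumed hit rates and an unchanged false alarm rate.

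The documents do not support saying that the primary claim cannot be separated from response bias. The TPR test is sound on this point; what is weaker is the support for reading a TPR difference as changed perception. This calls for a clear correction before analysis, since choosing the hit definition after seeing the data would be a data-dependent choice. It does not undermine the trial.

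**What to change.** In sections 5.5 and 11, define hits and misses separately for each intensity. Report d' and C for 90% versus catch trials as the versions that accompany the primary outcome, and for 110% versus catch trials separately. State that the false negative rate at 110% is not the complement of TPR.

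Because each block has only 10 catch trials, name one standard correction and apply it to every cell, not just those with extreme rates. The log-linear form adds 0.5 to each hit and false alarm count and 1 to each trial total. This may sit in the statistical analysis plan.

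The cost is wording only: the data are already collected by intensity, and no trial, session or participant is added. The trial mix need not change, since moving 110% trials to catch would cost precision at 110%. Nor should the reading of the primary result be made formally conditional on d'; reporting the matched d' and C beside TPR is enough.
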